## 5. MILESTONES

Milestone	Planned date
Start of data collection	01 November 2018
End of data collection	01 December 2018
Final study report	01 February 2019

This protocol was written post the conduct and completion of analysis.

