## 6. RATIONALE AND BACKGROUND

In the past 1–2 decades, treatment paradigms in rheumatoid arthritis (RA) have shifted dramatically from initial treatment with nonsteroidal anti-inflammatory drugs (NSAIDs), followed by cautiously progressive addition of disease-modifying antirheumatic drugs (DMARDs), to the current treatment approach of aggressive initiation of DMARD therapy soon after the diagnosis of RA has been made. This change in RA management results from increasing data supporting improved prognosis and outcomes with the initiation of DMARD therapy early in the course of symptomatic disease. Since the goals in RA management include not only disease remission, but also improved functional status, which is strongly associated with radiographic joint damage, an understanding of the impact that the initiation of appropriate treatment during early RA has on these outcomes is essential.

Accurate diagnosis of early RA begins with clear definitions of RA, as there is considerable variability in the literature regarding the time frame defining early RA. Previous intervention studies in early RA have included early RA as disease duration from 3 months to 3 years; however, with the knowledge of improved outcomes with earlier treatment in RA, it becomes clear that a shorter time interval for classification of early RA is clinically significant. Due to the wide range of definitions of early RA presented in the literature, it is difficult to characterize the specific time frame that defines early RA. However, it is now generally accepted that early RA is the onset of symptoms of joint (typically polyarticular) pain, stiffness, or swelling within the past 3 months, although in practical terms it may be difficult for rheumatologists to evaluate patients within that 3-month time frame, due to a variety of factors, including delay in referral of patients with early symptoms of inflammatory arthritis (IA) or delays in patients seeking medical attention for their symptoms.

Multiple studies have evaluated the benefits of early treatment of RA, including several that have evaluated the impact of early DMARD treatment on successful response to therapy. In particular, a meta-analysis of ~1,400 RA patients from 14 randomized controlled trials identified that one of the strongest predictors of response to therapy was a shorter disease duration at the time of treatment initiation.

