## 8. RESEARCH METHODS

### 8.1. Study Design

- **Retrospective analysis** of patients with RA that received etanercept from Baghdad teaching hospital (Rheumatology center) from 2012 until 2018 (inclusion and exclusion criteria will apply for selecting patients).
- **Primary aim:** determine the impact of early referral for management in patients with RA compared to delayed management.
- **Secondary aims:** Determine the influence of early referral on the response to biological treatment.

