### **8.3. Data Sources**

We identified patients in rheumatology registry with rheumatoid arthritis and obtained information on patient demographics (age, gender), education level (years), present smoking status, disease duration (years), current steroid therapy (yes/no), baseline DAS28 (Disease Activity Index 28) & CDAI (Clinical Disease Activity Index) RF (Rheumatoid factor) status, anticitrullinated protein antibody (anti-CCP) status. Primary Outcomes: Disease activity Index (DAS28) and CDAI in last follow up visit.

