### **8.6. Data Analysis**

Categorical covariates described by frequency distribution while continuous covariates expressed in terms of their mean and standard deviation or median and interquartile range as appropriate. Patients were divided according to the mean of disease duration groups (below and above mean) and unadjusted comparisons between groups of the covariates and the outcomes are evaluated using chi2 tests for categorical data, while for continuous data, we used the student's t-test for normally distributed variables and the Kruskall-Wallis test for non-parametric data.

We determined the effect of early referral on the biologic treatment response patients with RA a multivariate analysis by using a stepwise linear regression models. The response variable is defined as DAS28 and CDAI at last visit. The baseline variables considered demographic data, disease duration (years), methotrexate (yes/no), Current steroid therapy (yes/no), baseline DAS28 and CDAI, RF positive (yes/no), anti-CCP (yes/no), present smoking (yes/no).

We determined the effect of early response by using the difference between the base line DAS28 and CDAI. P value <0.05 considered statistically significant.

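### The primary outcome is read at each patient's last visit, so the early-versus-delayed comparison refers to no common time since etanercept start, and it is also biased if timing or start year differs between the groups

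*Combined protocol and SAP*

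**What the plan says.** Section 8.3 (Data Sources) names as primary outcomes "Disease activity Index (DAS28) and CDAI in last follow up visit". Section 8.6 (Data Analysis) carries the rule into the model: "The response variable is defined as DAS28 and CDAI at last visit". Neither section ties the last visit to a month or a window.

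Eligibility sets a floor only. The study population text in section 8.2 asks for one year or more of follow-up from the first biologic, and section 8.2.2 excludes patients with under a year of etanercept. Section 8.1 covers patients who received etanercept "from 2012 until 2018", section 8.2 says the registry opened in 2012, and section 5 dates the milestone "End of data collection" at 01 December 2018.

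Under section 8.6, patients are split at the mean disease duration and compared without adjustment, and a stepwise linear regression follows. Its candidate list reads "The baseline variables considered demographic data, disease duration (years), methotrexate (yes/no), Current steroid therapy (yes/no), baseline DAS28 and CDAI", then RF, anti-CCP and smoking. Calendar year of etanercept start is not on it. No summary of follow-up by disease-duration group is planned, and section 8.8 mentions missing data as the only limitation. Section 5 also records: "This protocol was written post the conduct and completion of analysis".

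**The concern.** There are two layers, and they need different amounts of support.

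The first needs no assumption about the groups. With a floor and no ceiling, one comparison can mix a score taken about a year after start with one taken several years later. A reader cannot say whether the result describes response at one year, at three, or at six.

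The second is conditional. Suppose that time from start to last visit, or calendar year of start, differs between the below-mean and above-mean groups, and that disease activity changes with time. Then part of any difference between the groups reflects when patients were measured or when they started, not how early they were treated. This could favour either group. Nothing planned would reveal it, because neither follow-up nor start year is tabulated by group.

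The absence of follow-up length from the baseline covariates is not itself a fault. It is a post-baseline quantity and does not belong in that list.

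**Working it through.** The plan gives no follow-up range, sample size, SD or effect size, so it has no figure of its own to reproduce.

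**Possible range of the last visit.** Inputs: the 1-year floor (sections 8.2 and 8.2.2), the planned end date of 01 December 2018 (section 5), and starts in 2012 or later (an assumption based on sections 8.1 and 8.2). Maximum time since start = end date minus start date:

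| Start year | Start 31 December | Start 1 January |
|---|---|---|
| 2012 | 5.92 years | 6.92 years |
| 2013 | 4.92 | 5.91 |
| 2014 | 3.92 | 4.91 |
| 2015 | 2.92 | 3.92 |
| 2016 | 1.92 | 2.92 |
| 2017 | floor of 1.0 applies | 1.91 |

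The range is therefore 1.0 to at most 5.92 or 6.92 years, depending on when in 2012 the first patient started. The ceiling falls with start year, so start year and timing are linked by construction.

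**Illustration of bias.** Every input here is assumed. Spurious difference = drift per year × gap in mean follow-up.

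- 0.05 × 0.5 = 0.025 DAS28 units
- 0.1 × 0.5 = 0.05
- 0.1 × 1 = 0.1

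For the unadjusted comparison, take SD 1.2, n per group (equal groups) and a two-sided 5% z test. Then SE = 1.2 × √(2/n), and the false-positive rate is 1 − Φ(1.96 − d/SE) + Φ(−1.96 − d/SE):

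| n per group | SE | d = 0.025 | d = 0.05 | d = 0.1 |
|---|---|---|---|---|
| 50 | 0.240 | 5.1% | 5.5% | 7.0% |
| 100 | 0.170 | 5.2% | 6.0% | 9.1% |
| 200 | 0.120 | 5.5% | 7.0% | 13.3% |

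For CDAI these rates hold only if its drift in SD units is the same: 0.05/1.2 = 0.04 to 0.1/1.2 = 0.08 SD per year. The effect on the regression was not computed.

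**How large is a 1-year gap?** If follow-up is uniform over the possible range, its SD is 4.92/√12 = 1.42 to 5.92/√12 = 1.71 years, so the gap is 1/1.71 = 0.59 to 1/1.42 = 0.70 SD. That is a large imbalance.

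**Balanced timing.** The spurious difference is drift × 0 = 0. The only cost is extra outcome variance: (0.05 × 1.42)²/1.2² = 0.4% to (0.1 × 1.71)²/1.2² = 2.0%.

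**What adjusting for start year can do.** Assume starts spread evenly from January 2012 to 1 December 2017. Calendar year of start explains about 97% of follow-up variance if everyone is seen up to the end date. It explains about 42% if last visits are spread evenly between 1 year and that date.

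**The case against.** The strongest reply is that bias is not shown. It needs both unequal timing and a change in disease activity with time, and the documents give neither. That stands. A reader might infer from section 6, which says that "treatment paradigms in rheumatoid arthritis (RA) have shifted dramatically", that the below-mean group started later and so had shorter follow-up. The documents do not support this: the passage describes DMARD practice in general and says nothing about disease duration at start in this registry.

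The upper illustration is also generous. If last visits are spread evenly between 1 year and the end date, the SD of follow-up is 1.30 years and a 1-year gap is 1/1.30 = 0.77 SD. In that case only half of a difference in start date carries over to follow-up, so the gap needs a 2-year difference in mean start date. Two equal halves completely separated by start date would differ by only 5.92/2 = 2.96 years. The 13.3% figure further needs 200 patients per group, and section 8.4 gives no size.

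Two further cautions stand. The range is what the dates permit, not what was observed, and it measures time since start rather than time on treatment, because no passage requires etanercept to be ongoing at the last visit. Section 8.1 also speaks of patients who received etanercept, so starts before 2012 are not strictly ruled out; they would widen the range.

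One could add that a last-visit outcome is a natural choice for registry data. Even so, its timing needs to be reported by group, and that is not planned. None of these replies supplies a common time point.

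**Conclusion.** The point holds in two parts. Without any assumption about the groups, the primary estimate refers to no common time since etanercept start. With starts in 2012 or later and the planned end date, readings can lie from about 1 year to at most about 5.9 to 6.9 years after start.

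Bias in the early-versus-delayed comparison is conditional on a difference in timing or start year between the groups together with change in disease activity over time. Its direction and size are unknown, and it is zero from this source if timing is balanced. The illustrated false-positive rates, from 5.1% (negligible) to 13.3%, rest wholly on assumed drift, gap, SD and group size, and cover the unadjusted test only. They are not an estimate for this study, and it would be wrong to conclude from them that the reported result is confounded.

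This should be fixed: a score near 12 months fits the plan's own eligibility floor, and tabulating timing by group would show whether the conditional part matters.

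**What to change.** Because the analysis was complete before the protocol was written, label all of the following post hoc. Keep the last visit as the declared primary outcome and show the original result beside the additions.

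1. Report time from etanercept start to last visit (median, interquartile range, range) and calendar year of start, by disease-duration group.
2. If the registry holds the scores, analyse DAS28 and CDAI at the visit closest to 12 months after start, within a stated window (for example 9 to 15 months). Give the number in each group with no visit in the window.
3. Add a last-visit model with calendar year of start forced in and not left to stepwise selection. Use time since start only in a sensitivity model: it is post-baseline and may depend on response, so adjusting for it can itself introduce bias. This step is a partial remedy, as the 97% and 42% shares show.
4. If 12-month scores do not exist, do steps 1 and 3 and state in section 8.8 that the outcome has no common time point.

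The cost is a further registry export and a re-run of the models. Section 8.3 lists no visit dates or interim scores among the data obtained, and the registry's longitudinal design does not prove that they are held, so availability must be checked. Steps 1 and 3 need only start and visit dates. Step 2 loses patients with no visit in the window, which adds to the missing-data limitation. The documents give no visit interval, so that loss cannot be predicted; if regular 9- or 12-month visits are counted from baseline and kept, it is nil.

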### **8.4. Study Size**

There is no pre identified study size. All patients that met the criteria entered for study.

### **8.5. Data Management**

The data structured and exported in excel sheet.

### **8.6. Data Analysis**

Categorical covariates described by frequency distribution while continuous covariates expressed in terms of their mean and standard deviation or median and interquartile range as appropriate. Patients were divided according to the mean of disease duration groups (below and above mean) and unadjusted comparisons between groups of the covariates and the outcomes are evaluated using chi2 tests for categorical data, while for continuous data, we used the student's t-test for normally distributed variables and the Kruskall-Wallis test for non-parametric data.

We determined the effect of early referral on the biologic treatment response patients with RA a multivariate analysis by using a stepwise linear regression models. The response variable is defined as DAS28 and CDAI at last visit. The baseline variables considered demographic data, disease duration (years), methotrexate (yes/no), Current steroid therapy (yes/no), baseline DAS28 and CDAI, RF positive (yes/no), anti-CCP (yes/no), present smoking (yes/no).

We determined the effect of early response by using the difference between the base line DAS28 and CDAI. P value <0.05 considered statistically significant.

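### Section 8.6 tests outcomes on a sample-mean split of disease duration, while stepwise selection may drop duration in years from the regression; the two codings are not explicitly ranked

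*Combined protocol and SAP*

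**What the plan says.** Section 8.6 uses disease duration in two ways.

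- **Group tests.** "Patients were divided according to the mean of disease duration groups (below and above mean". Between these groups, "unadjusted comparisons between groups of the covariates and the outcomes are evaluated using chi2 tests for categorical data", with a t-test or Kruskal-Wallis test for continuous data. Outcomes are therefore tested on the split, and the cut is not stated in years.
- **Regression.** The effect of early referral on response is determined by "a multivariate analysis by using a stepwise linear regression models". For the outcome, "The response variable is defined as DAS28 and CDAI at last visit". The candidates are introduced as follows: "The baseline variables considered demographic data, disease duration (years), methotrexate (yes/no". Duration is listed in years, no below/above-mean indicator is listed, and nothing says that duration stays in the model whatever the selection does.

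The significance rule is common to both: "P value <0.05 considered statistically significant". A closing sentence on differences from baseline names no coding of duration.

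Elsewhere, the hypothesis in Section 8.2 contrasts early with delayed referral and gives no threshold. Section 8.4 says that no study size was set in advance. Section 5 says that the protocol was written after the analysis was complete. As background, Section 6 reports the generally accepted view that "early RA is the onset of symptoms of joint (typically polyarticular) pain, stiffness, or swelling within the past 3 months". It also notes that earlier studies used durations from 3 months to 3 years, and that 3 months may be hard to achieve in practice.

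**The concern.** The hypothesis is a two-group statement, and the mean split is the only place where two groups are formed. Its threshold is a by-product of who is in the registry extract. Another centre applying the same rule would get another cut, and a few very long durations would raise the mean and move patients into the lower group.

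The regression does not have this weakness, but it has another: the exposure of interest is treated as an ordinary stepwise candidate. If selection removes it, the regression reports no estimate for duration, and the unadjusted split comparison is all that is left to answer the question.

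If both results are reported and disagree, no sentence says in terms which of them decides. Because the protocol postdates the analysis, prespecification does not guard against choosing between them.

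**Working it through.** **Inputs.** The documents give no mean, SD or shape for disease duration, and no sample size, power or effect size. There is therefore no figure of the plan's own to reproduce. The following are assumptions: the shape of duration, an effect linear in years (except where stated), a two-sided 0.05 test (Section 8.6 does not state sidedness) and, for the power column, a continuous analysis that would have 80% power.

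**Step 1: information kept by a split at the mean.** With X the duration, m its mean and p = P(X > m), and an effect linear in X, the share kept is the squared correlation between X and the indicator X > m:

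kept = (E[(X − m)+])² / (Var(X) · p(1 − p)), and loss = 1 − kept.

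- Uniform on 0 to 1: (1/8)² / ((1/12) × 0.25) = 0.75, so the loss is 25.0%.
- Normal: 0.3989² / 0.25 = 2/π = 0.637, so the loss is 36.3%.
- Exponential: p = e⁻¹ = 0.368; 0.368² / (0.368 × 0.632) = 0.582, so the loss is 41.8%.
- Lognormal with log-SD s: kept = (2Φ(s/2) − 1)² / ((exp(s²) − 1) · p(1 − p)), with p = Φ(−s/2). For s = 0.8 this is 0.3108² / (0.8965 × 0.2258) = 0.477, so the loss is 52.3%.

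**Step 2: what this does to power.** Power of the split test = Φ(2.80 × √kept − 1.96), where 2.80 = 1.96 + 0.84. For the normal shape, 2.80 × √0.637 − 1.96 = 0.275 and Φ(0.275) = 61%.

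| Assumed shape | Share below the mean | Information lost | Power of split test (continuous test at 80%) |
|---|---|---|---|
| Uniform | 50.0% | 25.0% | 68% |
| Normal | 50.0% | 36.3% | 61% |
| Gamma, shape 2 | 59.4% | 39.2% | 59% |
| Exponential | 63.2% | 41.8% | 57% |
| Lognormal, log-SD 0.8 | 65.5% | 52.3% | 49% |
| Lognormal, log-SD 1.0 | 69.1% | 60.0% | 43% |
| Lognormal, log-SD 1.2 | 72.6% | 68.2% | 35% |

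**Step 3: finite samples.** In simulation with an assumed n of 200, splitting at the sample mean gave average losses of 36.1% (normal), 40.9% (exponential), 49.4% (lognormal 0.8) and 54.5% (lognormal 1.0). These are close to the large-sample values or somewhat below them.

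**Step 4: sensitivity to the linearity assumption.** Suppose the effect is linear in log duration and duration is lognormal with log-SD 0.8. The mean then lies at z = 0.8/2 = 0.4 on the log scale. Kept = φ(0.4)² / (p(1 − p)) = 0.1356 / 0.2258 = 0.60, so the loss is about 40% rather than 52%, and the power is Φ(2.80 × √0.60 − 1.96), about 58%. If the true effect were a step exactly at the cut, the split would lose nothing.

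**Step 5: where the loss applies.** The regression uses years, so none of these losses applies to it. Its separate weakness, that selection may remove duration, needs no distributional assumption.

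**The case against.** The strongest reply is that Section 8.6 already determines the effect of early referral with a continuous duration variable, and that the split serves only comparisons which the plan itself calls unadjusted. Much of this stands, and it rules out several stronger readings that a reader might infer.

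- **That the split is the early-versus-delayed analysis and the regression merely confirms it.** Section 8.6 attaches the word early to the regression and describes the split only as below and above the mean. Nothing says that one confirms the other.
- **That the study's effect estimate loses 36% to 52% of its information.** Only the unadjusted group tests are affected. The percentages depend on assumed shapes and on linearity in years, and the 80% starting power is hypothetical.
- **That the two analyses test different exposures.** They are two codings of one variable, disease duration.
- **That the split breaks the protocol's own definition of early.** The 3-month statement in Section 6 is background about symptom onset. It stands beside a wider range and a caveat on feasibility, and it is not an analysis definition.

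The reply does not remove three points. Outcomes are still tested at the 0.05 level on a cut that depends on the sample and is not reported. Determining the effect by stepwise selection does not ensure an estimate for duration. The order of the two analyses is left to inference.

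**Conclusion.** The point holds as a weakness of method that is cheap to remove. Three facts rest on the text alone: the cut is set by the sample and not given in years, duration is a stepwise candidate that may be dropped, and the two codings are not explicitly ranked.

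The size is conditional. Under an effect linear in years, the split tests lose about 36% (normal) or about 42% to 52% (exponential to lognormal with log-SD 0.8), within a wider range of 25% to 60% or more. For that same lognormal shape, an effect linear in log duration lowers the loss to about 40%. The documents do not show which case applies. They do not support a claim that the regression is underpowered for this reason, or that the two analyses did in fact disagree.

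**What to change.** In Section 8.6:

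1. Name continuous disease duration at etanercept start as the single main exposure, on one stated scale (for example log years, with a spline as a sensitivity check). If log years is chosen, say how any duration recorded as zero is handled.
2. Force this term into every DAS28 and CDAI outcome model, whatever the stepwise selection does with the other candidates, and report its estimate with a confidence interval.
3. Keep the mean split as descriptive only, report its cut in years, and call the groups shorter and longer duration.

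The cost is a change of wording and a re-run of models on data already in hand. Since the protocol was written after the analysis, the report should say that this specification was fixed afterwards. The downside is an effect estimate that is slightly less simple to present than a difference between two groups.

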#### Hypothesis

Our initial hypothesis is that there is no difference in response between early and delayed referral to biological treatment.

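### Timing is tested on each outcome by an unadjusted mean split and by a stepwise regression under one p<0.05 rule, so a confounded unadjusted result can stand as the study's timing finding

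*Combined protocol and SAP*

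**What the plan says.** Section 8.6 contains two analyses of timing on the same outcomes.

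- **Mean split.** "Patients were divided according to the mean of disease duration groups (below and above mean"). The comparisons that follow are unadjusted and expressly cover the outcomes as well as the covariates: "unadjusted comparisons between groups of the covariates and the outcomes are evaluated using chi2 tests for categorical data". DAS28 and CDAI are scores, so the next clause governs them: "for continuous data, we used the student's t-test for normally distributed variables and the Kruskall-Wallis test for non-parametric data".
- **Regression.** "We determined the effect of early referral on the biologic treatment response patients with RA a multivariate analysis by using a stepwise linear regression models". Its dependent variables are the last-visit DAS28 and CDAI scores, which section 8.3 names as the primary outcomes. Duration enters as one item in a candidate list: "The baseline variables considered demographic data, disease duration (years), methotrexate (yes/no") and so on. Nothing says it is forced in, and no entry or removal rule is given.

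A single threshold closes the section: "P value <0.05 considered statistically significant". The hypothesis in section 8.2 is that "there is no difference in response between early and delayed referral to biological treatment"; it is not tied to either analysis. Section 8.4 gives no study size. Section 5 states that the protocol was written after the analysis had been completed.

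**The concern.** The two analyses answer different questions. The split compares two groups, cut at a sample-dependent mean, with no adjustment. The regression estimates an adjusted change in score per year of duration. The hypothesis is worded as a two-group contrast, which only the split tests, while the sentence about determining the effect of early referral belongs to the regression.

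Patients were not randomised to early or late treatment, so the unadjusted comparison takes in whatever else differs between short- and long-duration patients. If it is significant and the adjusted effect is null, nothing in the plan stops the unadjusted p-value from being reported as an effect of early etanercept. If stepwise selection has removed duration, the regression offers no coefficient or interval to set against it.

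**Working it through.** **1. The text.** The plan states no error rate, power or sample size, so there is no figure of its own to reproduce. Set side by side:

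| | Mean split | Regression |
|---|---|---|
| Exposure | Below/above mean duration | Duration in years |
| Adjustment | None | Stepwise-selected covariates |
| Outcome | DAS28, CDAI | DAS28, CDAI at last visit |
| Threshold | p<0.05 | p<0.05 |
| Matches the 8.2 hypothesis | Yes (two groups) | No (slope) |
| Described as determining the effect | No | Yes |

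No section ranks the two or calls either one descriptive.

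**2. Two tests, no confounding, no effect, one outcome.** If the tests were independent, the chance of at least one p<0.05 would be 1 − 0.95² = 0.0975. For two correlated normal tests it is 0.091 at correlation 0.5, 0.078 at 0.8 and about 0.07 at 0.9. A simulation (2,000 datasets per setting, n=100) gave split 0.050, stepwise slope 0.056 and both 0.016. Hence either = 0.050 + 0.056 − 0.016 = 0.090, and exactly one = 0.090 − 0.016 = 0.074. At n=300 the either-test rate was 0.086.

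**3. One confounder, no effect of duration.** All inputs here are assumptions. Let log duration be normal with SD s, and let the confounder (SD 1) have correlation r with log duration and coefficient b on an outcome with SD σ.

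- The mean of a log-normal variable lies s/2 SDs above its median on the log scale, so the proportion below the cut is P = Φ(s/2).
- Group difference in standardised log duration: d = φ(s/2) / [P(1 − P)].
- Spurious outcome difference: Δ = b·r·d.
- SE = σ / √[nP(1 − P)].
- Rejection rate = Φ(Δ/SE − 1.96) + Φ(−Δ/SE − 1.96).

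*Setting A:* s=0.9, b=0.3, r=0.4, σ=1. P=0.674, P(1 − P)=0.220, d=0.3605/0.220=1.64, Δ=0.3 × 0.4 × 1.64=0.197.

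- n=100: SE=0.213, ratio 0.92, rejection 15.2% (simulated 15.2%).
- n=300: SE=0.123, ratio 1.60, rejection 35.9% (simulated about 37%).

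With r=0.2 the simulated split rate falls to 9.0% at N=100, 10.3% at N=200 and 17.3% at N=400.

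*Setting B:* s=0.75, the confounder is baseline DAS28 with b=0.5 and r=0.3, residual SD 1.1, so σ=√(0.25 + 1.21)=1.208. d=1.626, Δ=0.5 × 0.3 × 1.626=0.244.

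- n=100: SE=0.253, ratio 0.97, rejection 16.2% (simulated 15.5%).
- n=300: SE=0.146, ratio 1.67, rejection 38.7% (simulated 38.6%).

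In the same simulated datasets the stepwise duration test rejected in about 5% to 6%.

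**4. What the stepwise model leaves behind.** With no true effect, selection at conventional thresholds removed duration in about 94% to 96% of simulated datasets. In those, the split is the only timing result. Selection does not always hold 5% either: with b=0.2, r=0.6 and N=100, the stepwise duration test rejected in 9.7%, against 5.5% in a full model with duration forced in.

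**5. Direction.** Both tests significant with opposite signs occurred in at most 0.003 of datasets in any setting.

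**The case against.** The strongest reply is that the plan already gives the two analyses different roles. The paragraph with the split begins descriptively and calls its comparisons unadjusted; the next paragraph introduces the regression as the way the effect was determined. Crude and adjusted results are expected to differ in registry data, which is why both are shown.

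Much of this stands. The text does lean towards the regression, and a reader who infers that the plan gives no indication at all of which analysis matters goes too far. But the lean is not a ranking. The regression sentence concerns response to biologic treatment, which echoes the secondary aim in section 8.1, while the primary aim, the objective in section 7 and the hypothesis are all early-versus-delayed contrasts.

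Four other stronger readings are not supported:

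- **The two analyses would point in opposite directions.** The realistic disagreement is significant against not significant.
- **The plan lets any p<0.05 reject the hypothesis.** No such rule is written; the gap is that none excludes it.
- **There is a third timing test on change from baseline.** The closing sentence on a baseline difference mentions neither duration nor the two groups, so this would be a guess.
- **The 15% to 37% is multiplicity.** It is confounding of a comparison labelled unadjusted. The crude difference exists in such data; the error would be to read it as an effect of early treatment.

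**Conclusion.** The point holds for each outcome taken alone, separately from the use of two outcomes. Section 8.6 runs an unadjusted and an adjusted timing test under one threshold, and the hypothesis fits the unadjusted one. It is more than a missing label, because stepwise selection usually removes a null duration effect and leaves the unadjusted comparison unopposed.

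The inflation from having two tests is modest, about 0.07 to 0.09 against 0.05, and arises only if either result may decide. The larger exposure is confounding: about 15% at n=100 to 37% at n=300 in setting A, and less with a weaker confounder. Sample size, the distribution of duration and the strength of the confounder are all assumed, so these figures show scale only; the finding rests on the text. The documents do not show which result the study report emphasised.

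**What to change.** In section 8.6 and in the study report:

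1. For each outcome, judge the hypothesis on the disease-duration coefficient, with its 95% CI, from a linear model that always keeps disease duration and the listed baseline covariates, with no stepwise removal of duration. Naming the present stepwise model as decisive would not be enough, because it often yields no duration coefficient.
2. Report the below/above-mean outcome comparison as descriptive, with no claim of an effect of early treatment.
3. Word the hypothesis in section 8.2 to match, for example no association between disease duration and last-visit response after adjustment.
4. Report both results and state that this ordering was chosen post hoc, since the protocol followed the analysis. The change makes the reporting transparent; it cannot restore a prespecified 5% level.

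The cost is a few sentences in 8.2 and 8.6, one refitted model per outcome and matching report wording, with no new data. The small downside is that a significant unadjusted comparison can no longer be presented on its own as a positive finding.
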